1. BACKGROUND AND SIGNIFICANCE

Primary liver cancer is the world's third most common cause of cancer death. In the United States -unlike other malignancies such as breast, prostate and lung cancer- the incidence of hepatocellular carcinoma (HCC) is increasing. The present gold standard, for the less than a third of the HCC patients who are medically fit and technically resectable, is HCC resection or liver transplant. For the patients who are not operative either due to underlying liver disease with associated liver dysfunction or other comorbidity, a number of non-operative treatments are available for treatment including percutaneous tumor ablation (i.e. radiofrequency ablation [RFA], microwave ablation (MWA), percutaneous ethanol injection [PEI], cryotherapy). In addition newer external beam radiotherapy techniques, such as hypo-fractionated image guided radiation therapy (HIGRT) –also known as stereotactic body radiotherapy (SBRT)–, have been used in the treatment of these patients.

Percutaneous local ablation (PLA) selectively targets the tumor with an additional intentional margin of 0.5-1cm of non-cancerous liver tissue and induces tumor cell death, most often via coagulative necrosis. Local application of chemical agents or microwave/radiofrequency waves does not induce systemic effects and is typically performed under real-time ultrasound or CT guidance using local anesthesia and conscious sedation or general anesthesia. Worldwide, RFA is the most commonly used ablation technique. In the US, MWA is quickly becoming the preferred modality of PLA. MWA induces thermal injury through the delivery of electromagnetic energy and the application of rapidly alternating microwave frequency current leads to coagulative necrosis of tissue. Compared with RFA, MWA appears to be more effective for lesions in close proximity to the portal or hepatic veins; heat sink is less of an issue given increased speed with which therapy can be delivered. Additionally, tumor sizes >3cm sometimes can be effectively treated with MWA. A recent meta-analysis comparing RFA to MWA for primary HCC showed they had similar efficacy¹, however, MWA appeared to have improved local tumor control over RFA in the treatment larger tumors.

Advances in radiotherapy simulation, treatment planning and delivery integrated together collectively termed HIGRT or SBRT, have facilitated safe dose escalation to HCC. A number of small, single institutional prospective studies have evaluated the use of HIGRT for treatment of HCC. These experiences suggest that HIGRT is well tolerated and yields excellent local control rates, however, follow up is short and thus many institutions and consensus guidelines favor ablation for early stage HCC patients who are not surgical candidates. The benefits of HIGRT are that it is a non-invasive, outpatient procedure typically delivered in 3-10 fractions. Although no randomized studies have compared HIGRT with other local therapies, in retrospective analysis outcomes appear comparable², warranting further evaluation.

Health-related quality of life for patients with HCC is important. QOL targets are important post-treatment metrics; previous studies have shown that both pretreatment QOL³ and post-treatment QOL⁴ have been associated with overall survival in various cancers. While both PLA and SBRT can ablate tumors, they do have known impacts on patients' QOL. QOL has recently been reported as a clinically important target in patients treated with HIGRT for HCC. A randomized study evaluating the use of PLA in patients with metastatic colorectal cancer evaluated health related QOL as a secondary endpoint via the EORTC QLQ-30 questionnaire at baseline and every 6 weeks. Mean global QOL dropped 27 points approximately 6 weeks post PLA and recovered to near baseline shortly thereafter⁵. QOL was also assessed in a prospective evaluation of SBRT for primary intrahepatic malignancies using the EORTC QLQ-30 and the Functional Assessment of Cancer Therapy-Hepatobiliary (FACT-Hep) at baseline and 1, 3, 6, and 12 months post-treatment. While appetite and fatigue domains dropped markedly at 1 month post-SBRT, global QOL remained stable at this time point. Baseline FACT-Hep and EORTC-QLQ scores were associated with improved survival in this analysis⁶.

There are unique challenges within the VA patient population specifically with regards to the effective and efficient treatment of HCC. The VA has a higher portion of HCC patients than the average US population given higher base rates of HCV infection and alcoholic cirrhotic liver disease. Transplant options are limited due to extensive co-morbidities. Lack of easy access to a transplant center also creates geographic access issues. New limits on the Model for End Stage Liver Disease (MELD HCC) exception scores (now capped at 34 as of October 8, 2015) are already reducing overall transplant candidacy for many HCC patients. Alternative treatments to transplant and surgery based on strong evidence-based medicine are essential. This is particularly true in a new era of curative HCV treatment which -when combined with non-transplant based therapies for HCC- would potentially obviate the need for any additional therapies and break the cycle of cirrhosis, cancer and mortality.

2. PROTOCOL SYNOPSIS AND RESEARCH SUMMARY

2.1 Purpose

Given that many patients with HCC are not surgical candidates (for either resection or transplant), PLA techniques have become the standard non-operative approach. Non-randomized data have shown that the local control of HIGRT is comparable to that of PLA. Direct comparison of these two modalities via a randomized controlled clinical trial is the next logical step.

This research protocol will directly compare Percutaneous Local Ablation (PLA) to Hypofractionated Image-Guided Radiation Therapy (HIGRT) for patients with Hepatocellular Carcinoma (HCC) who are not surgical candidates or decline surgery while undergoing care at the Durham VA or at Duke Cancer Center.

Primary Objective

To compare change in Quality of Life (QOL), as defined by the European Organization for Research and Treatment of Cancer Quality of Life Questionnaire Core-30 (EORTC C-30), from baseline to 1 month post treatment in patients receiving PLA vs HIGRT.

Secondary Objectives

1. To estimate the difference in change in QOL in patients receiving PLA vs HIGRT, as measured EORTC C-30, from baseline to 3 months post-treatment
2. To estimate the difference in change in QOL in patients receiving PLA vs HIGRT, as measured EORTC C-30, from baseline to 6 months post-treatment
3. To estimate the difference in change in QOL in patients receiving PLA vs HIGRT, as measured by FACT-Hep, from baseline to 1 month, baseline to 3 months and baseline to 6 months post-treatment
4. To assess for grade ≥ 2 acute toxicity within 90 days of treatment initiation
5. To estimate the total healthcare system cost associated with PLA vs HIGRT from time of intervention through 90 days post treatment

Exploratory Objectives

1. To assess for grade 3+ late toxicity (>90 days post ablative therapy or radiation therapy)
2. To evaluate local control at the treated site within the liver
3. To evaluate distant liver recurrence (intrahepatic lesions other than treated lesion)
4. To evaluate median progression free survival (PFS)
5. To evaluate median overall survival (OS)

Hypotheses

For the primary endpoint of change in QOL at 1 month post treatment versus baseline, HIGRT will have significantly better patient reported global QOL than PLA.

2.2 Design and Procedure

This is a phase II, randomized trial comparing PLA vs HIGRT in non-surgical HCC patients at the Durham VA and the Duke Cancer Center.

2.2.1 Selection of Subjects/Subject recruitment

Patients who are potentially eligible for study enrollment will be identified within Radiation Oncology, Radiology, GI and GI oncology clinics. Patients could potentially be identified at multi-disciplinary Liver Tumor Board. The treating gastroenterologist, radiologist, radiation oncologist, medical oncologist or surgical oncologist (or their extenders) will introduce the study to patients, and if the patient is interested he/she will meet with a clinical trials coordinator for further details and consent.

2.2.2 Duration of Study

Patients will be on study therapy for approximately 6 months. The end of study participation will be at the completion of the 6 month survey, approximately 180 days post treatment (+/- 30 days). Thereafter patients will continue to be followed by the treating physician as per standard of care for follow up care and long-term follow up information will continue to be collected through review of the electronic health record.

2.2.3 Data Analysis and Statistical Considerations

Ninety patients will be randomized with equal allocation to the two arms. Randomization will be stratified by whether the baseline global QOL score is < 60 or ≥ 60 , where QOL is measured by the EORTC QLQ-C30 scale (i.e., the European Organization for Research and Treatment of Cancer Quality of Life Questionnaire Core-30) which has a score range of 0-100. The primary outcome is the change in QOL from baseline to 1 month. We anticipate that approximately 10% of the accrued patients will be withdrawn before 1 month, leaving 80 evaluable patients to be used in the statistical analyses. The general linear model will be used to test for an arm effect (in patients receiving PLA vs HIGRT) by regressing the change in QOL on arm, controlling for the baseline value of QOL and the Child Pugh score. To calculate the power of the arm effect (in patients receiving PLA vs HIGRT) on change in QOL, we first note that the standard deviation of a normally distributed change score (SD_c) depends upon the SD of the pre-score, the SD of the post-score, and the Pearson correlation (ρ) between the two scores. If the SD's of the pre-score and the post-score are assumed equal and the correlation between them is 0.50, then $SD_c = SD$. For purposes of the power calculation, we assume that $SD=10$ and $\rho = 0.5$; therefore $SD_c = 10$. Assuming 40 evaluable patients per arm, the two-sample t-test (1-sided alpha = 0.10) of an arm difference in change across time in QOL has power 0.82 when the true arm difference in change score is 5 (i.e., 50% of SD_c). An arm difference of 50% of a standard deviation of an outcome variable is generally considered to be a "medium"-sized effect. In order to have 80 evaluable patients, 90 patients will be accrued (assuming ~10% drop out prior to the 1 month EOTRC QOL-C30 questionnaire).

After randomization, patients who have consented to study, but in the clinical judgement of the treating physician are no longer candidates for the randomized treatment, will continue to be evaluable for all study endpoints if treated with MWA or HIGRT (per PI approval). The primary analysis will be intent-to-treat (i.e., treatment arm as randomized). A sensitivity analysis will be conducted with patients categorized by treatment received.

At Duke and the VAMC respective liver multi-disciplinary conferences meet 2-4 times a month and there are typically 3-4 patients presented at each tumor board who may be potentially eligible for this study. We anticipate accruing 20-30 patients annually.

As a secondary objective, the arm difference in the change in QOL from baseline to month 1 as measured by the Functional Assessment of Cancer Therapy-Hepatobiliary (FACT-Hep, version 4) will be calculated with its 95% confidence interval.

Please see section 5 below for more information regarding secondary and exploratory objectives.

3. STUDY ARMS

3.1 Radiation Therapy (experimental arm)

Hypo-fractionated image guided radiation therapy (HIGRT) refers to delivery of highly precise, conformal radiation therapy with high dose per fraction using image guidance to ensure proper tumor localization with each fraction. When it is given in 1-5 fractions, it is sometimes called stereotactic body radiation therapy (SBRT). For the purposes of this clinical trial, we will refer to the treatment as HIGRT at all times. It is believed that HIGRT results in an improved therapeutic ratio over traditional radiation therapy, and HCC tumor control rates as high as 70-90% at 1-2 years have been reported^{8,9}.

3.1.1 Clinical experience

HIGRT represents the only non-invasive curative modality in the management of HCC. HCC patients typically have a host of other medical comorbidities complicated by underlying liver dysfunction that makes the implementation of liver-directed therapy challenging. Presently HIGRT is typically offered only after alternative surgical (transplantation/hepatectomy) and non-operative approaches (PLA/embolization) have been exhausted. An ongoing Phase III randomized study (RTOG 1112) is attempting to establish the role of HIGRT, in addition to sorafenib, in patients with locally advanced HCC who are not candidates for any of the aforementioned modalities. While this trial will contribute valuable data to the field of radiation oncology in the next 5-10 years, it does not help guide current clinical practice. For example, in early stage lung cancer, HIGRT has become the established alternative in patients who are deemed to be poor surgical candidates.

3.2 Percutaneous Localized Ablation (Microwave Ablation, control arm)

Microwave Ablation (MWA) is a form of percutaneous localized ablation using thermal ablation techniques to treat cancer via direct coagulative necrosis. Microwaves can generate high temperatures in a short period of time; MWA has the potential to improve treatment efficacy over radiofrequency ablation as it can be used to treat larger lesions and has less susceptibility to heat-sink due to vessel proximity. MWA uses electromagnetic waves (300 MHz to 300 GHz) to produce oscillation of polar molecules within tissue; this generates tissue necrosis through frictional heating. For HCC, one or more microwave antennae are inserted into the liver, usually under the guidance of ultrasonography or computed tomography (CT). Frequency and length of treatment is determined on a case by case basis depending on tumor size and proximity to vessels or other organs at risk. PLA is administered as a single treatment.

4. ENDPOINTS

QOL surveys such as European Organization for Research and Treatment of Cancer (EORTC) Quality of Life Questionnaire Core-30 (QLQ-C30) measure patient reported symptoms including fatigue, difficulties with activities of daily living (ADLs) and psychosocial needs. Specific liver QOL assessments such as the Functional Assessment of Cancer Therapy-Hepatobiliary (FACT-Hep) additionally assess liver-specific symptoms including jaundice, itching and abdominal pain.

Primary Endpoint:

The primary endpoint is change in global QOL score measured from baseline to month 1 post treatment. This change will be compared between treatment arms.

Higher average global QOL scores indicate better QOL. We hypothesize that the HIGRT arm will have significantly better QOL at month 1 than the PLA arm. A significantly greater drop in the average global QOL score at 1 month post treatment versus baseline is expected with PLA than with HIGRT, i.e., we expect the average change in the global QOL score to be less on HIGRT indicating higher QOL at 1 month post treatment with HIGRT.

Ninety patients will be randomized with equal allocation to the two arms. Randomization will be stratified by whether the baseline global QOL score is < 60 or ≥ 60 , where QOL is measured by the EORTC QLQ-C30 scale. We anticipate that approximately 10% of the accrued patients will withdraw before 1 month, leaving 80 evaluable patients to be used in the statistical analyses. The general linear model will be used to test for an arm effect (in patients receiving PLA vs HIGRT) by regressing change across time in QOL on arm, controlling for the baseline value of QOL, Child Pugh score, and time between baseline and end of treatment. To calculate the power of the arm effect (in patients receiving PLA vs HIGRT) on change in QOL, we first note that the standard deviation of a normally distributed change score (SD_C) depends upon the SD of the pre-score, the SD of the post-score, and the Pearson correlation (ρ) between the two scores. If the SD's of the pre-score and the post-score are assumed equal and the correlation between them is 0.50, then $SD_C = SD$. For purposes of the power calculation we assume that $SD=10$ and $\rho = 0.5$; therefore $SD_C = 10$. Assuming 40 evaluable patients per arm, the two-sample t-test (1-sided alpha = 0.10) of an arm difference in change across time in QOL has power 0.82 when the true arm difference in change score is 5 (i.e., 50% of SD_C). An arm difference of 50% of a standard deviation of an outcome variable is generally considered to be a "medium"-sized effect. In order to have 40 evaluable patients per treatment arm, 90 patients will be accrued (assuming drop out prior to the 1 month EORTC QOL-C30 questionnaire).

After randomization, patients may decline the randomized treatment but will continue to be evaluable for all study outcomes if treated with MWA or HIGRT. All endpoints will be analyzed per randomized arm and per treatment delivered. If the patient does not receive either SBRT or MWA, the patient will be withdrawn from the study.

Secondary Endpoints:

[figure not shown]
1. *To estimate the change in QOL in patients receiving PLA vs HIGRT, as measured by EORTC C-30, from baseline to 3 months post-treatment.* The mean difference between arms in change from baseline to 3 months in QLC-C30 will be estimated with their 95% confidence intervals [CI]. To calculate these CI's, the mean arm difference in QOL and its standard error will be estimated from a general linear model in which change in QOL is regressed on arm, controlling for the baseline value of QOL and the Child Pugh score.
2. *To estimate the change in QOL in patients receiving PLA vs HIGRT, as measured by EORTC C-30, from baseline to 6 months post-treatment.* The mean difference between arms in change from baseline to 6 months in QLC-C30 will be estimated with their 95% confidence intervals [CI]. To calculate these CI's, the mean arm difference in QOL and its standard error will be estimated from a general linear model in which change in QOL is regressed on arm, controlling for the baseline value of QOL and the Child Pugh score.

3. *To estimate the change in QOL as measured by FACT-Hep in patients receiving PLA vs HIGRT.* Change in FACT-Hep score from baseline to 1 month, baseline to 3 months and baseline to 6 months will be calculated for each patient, and the mean arm difference in change will be estimated with its 95% CI. The CI will be estimated as described for Secondary Objective 1.
4. *To estimate grade ≥ 2 acute toxicity within 90 days of treatment initiation.* CTCAE version 4 will be used for all toxicity assessments. The acute toxicity rate will be defined as any grade 2+ toxicity occurring during treatment through 90 days post-PLA or post-HIGRT. The acute toxicity rate with its exact 95% confidence interval will be estimated within each arm. The arm difference in acute toxicity rate will be estimated with its 95% CI. We will also estimate the rate of hospitalization due to treatment complications with its 95% CI and the proportion of patients requiring treatment breaks longer than 7 days from HIGRT, with its 95% CI.
5. *To estimate the total healthcare system cost associated with PLA vs HIGRT from time of intervention through 90 days post treatment.* Costs will be estimated based on national averages for billable charges for all codes associated with PLA vs HIGRT throughout the course of treatment and the post-treatment follow up. This includes costs associated with any hospitalizations related to either procedure. Total costs per arm will be described with boxplots. Arm differences in the health care cost will be estimated using the statistical method best suited to the observed distribution of cost in these data (for example, a single distribution generalized linear model specifying, perhaps, a Gamma distribution).

Exploratory Endpoints:

1. *To assess for late toxicity (>90 days post PLA or HIGRT).* Late toxicity will be defined as any Grade 3+ toxicity occurring after the completion of the treatment regimen up to 6 months post-PLA or HIGRT. The proportion of patients experiencing any type of late toxicity will be estimated with an exact 95% confidence interval, by arm.
2. *To evaluate local control at the treated site within the liver.* Time to local failure will be defined as the length of time from enrollment to local failure at the site of treated disease within the liver (within the PTV). Intrahepatic sites distinct from treated lesions and distant failures will be ignored and deaths will be censored. The distribution of time to local failure will be estimated with the Kaplan-Meier method, by arm.
3. *To estimate distant liver recurrence (intrahepatic lesions other than treated lesion).* Time to distant liver recurrence will be defined as the length of time from date of enrollment to intrahepatic failure not within the site of treated disease; distant failures will be ignored and deaths will be censored. The distribution of time to distant failure will be estimated with the Kaplan-Meier method, by arm.
4. *To estimate median progression-free survival (PFS).* PFS will be defined as the length of time from enrollment to local or distant failure or death, whichever comes first. The distribution of PFS will be estimated with the Kaplan-Meier method, by arm.
5. *To estimate median overall survival (OS).* Overall survival (OS) will be defined as the length of time from enrollment to death due to any cause. The distribution of OS will be estimated with the Kaplan-Meier method, by arm.

5. STUDY SCHEMA (Pooled patients from Durham VAMC and Duke)

6. SUBJECT ELIGIBILITY (Eligibility checklist will be used to confirm [VA patients only]: see Appendix)

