8.6 Treatment Planning/Target Volumes

CT images (ideally triphasic images) will be registered to MRI images (by soft tissue alignment) to assist in contouring the GTV. Registration will be performed with the best fit liver-to-liver image registration focusing on the region of the PTV if deformation or rotation occurs between scans.

The GTV represents the target lesion and should be identified on the arterial, portal venous, and delayed CT image sets (if multiple phase CT images are available) as well as on MRI images.

An ITV expansion of the GTV will be created to fully account for the magnitude of the motion observed in the 4D simulation evaluation. If multiple contrast phases are available from CT simulation these will be registered to bony anatomy to verify that the GTV remains encompassed by the ITV.

The ITV will be expanded by 5-10mm radially and 7-10mm superior/inferiorly to arrive at the PTV.

The treatment dose is 50 Gy in 5 or 10 fractions over 2 or 3 weeks, respectively. Lesions in close proximity to a GI structure (colon, small bowel, duodenum, stomach), in a patient with Child-Turcotte-Pugh (CTP) classification B, or a patient with prior radiotherapy to the abdomen will be treated with 50Gy in 10 fractions. Fractionation determination is at the discretion of the treating physician.

Conformal 3D or arc radiotherapy, IMRT or VMAT are acceptable methods of treatment delivery.

All patients must be imaged prior to treatment with volumetric imaging.

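### The primary model is stated two ways, and section 4 adds a post-randomisation covariate partly set by arm, so its arm coefficient may not be the declared intent-to-treat effect

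*Combined protocol and SAP*

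**What the plan says.** Section 2.2.3 specifies the primary test as "regressing the change in QOL on arm, controlling for the baseline value of QOL and the Child Pugh score". It also says: "The primary analysis will be intent-to-treat (i.e., treatment arm as randomized".

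Section 4 (Primary Endpoint) describes the same test, with the same sample size, alpha and power statement, but "controlling for the baseline value of QOL, Child Pugh score, and time between baseline and end of treatment".

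The 3- and 6-month models for the secondary QOL endpoints in section 4 use the shorter list: "change in QOL is regressed on arm, controlling for the baseline value of QOL and the Child Pugh score".

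No text ranks the two lists. The onward reference in section 2.2.3 covers only the other objectives: "Please see section 5 below for more information regarding secondary and exploratory objectives".

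On treatment delivery, section 3.2 states: "PLA is administered as a single treatment". For HIGRT, section 8.6 states: "The treatment dose is 50 Gy in 5 or 10 fractions over 2 or 3 weeks, respectively". It adds: "Fractionation determination is at the discretion of the treating physician".

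**The concern.** Two problems arise together.

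First, the primary test is not uniquely defined. One dataset can give two arm estimates and two p-values. If the choice is not fixed before anyone sees data by arm, the 1-sided error can exceed 0.10.

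Second, the two models need not estimate the same thing. Baseline QOL is the stratification factor, so it is measured before randomisation and end of treatment comes after it. The interval is therefore a post-randomisation variable, and part of it is a consequence of the assigned arm. Conditioning on it can remove part of the effect of assignment, or add a spurious component.

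The interval may also carry prognosis within the HIGRT arm. Section 8.6 links the 10-fraction course to Child-Turcotte-Pugh class B, proximity to a GI structure and prior abdominal radiotherapy. The Child Pugh covariate captures only part of that.

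**Working it through.** **Inputs from the plan (sections 2.2.3 and 4).** 40 evaluable patients per arm, difference 5, SD of change 10, pre-post correlation 0.5, 1-sided alpha 0.10, stated power 0.82.

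**Plan's own figure.** The noncentrality is 5 / (10 × √(2/40)) = 2.236. The exact t-test on 78 df gives power 0.827 (normal approximation 0.830), so 0.82 is reproduced. With baseline adjustment at correlation 0.5, the residual SD is 10 × √(1 − 0.25) = 8.66 and power is 0.901.

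**Inputs the plan does not give.** These are assumptions:
- D, the net arm gap in mean days from baseline to end of treatment (HIGRT minus ablation);
- s, the within-arm SD of that interval in days;
- b, the within-arm slope of QOL change in points per week.

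For scale, on consecutive weekdays the first and last of 5 fractions are 4 days apart (Monday start) or 6 days apart. For 10 fractions the figures are 11 or 13. Section 8.8 recommends completion within 2 and 3 weeks. The wait to treatment start is not given and could shrink, cancel or reverse the gap.

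**1. Precision, b = 0.** The arm-interval R² is (D/2)² / ((D/2)² + s²), and the variance inflation factor is VIF = 1/(1 − R²). For D = 14 and s = 14, R² = 49/245 = 0.20 and VIF = 1.25. The sign of D does not matter.

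**2. Choice between models, b = 0.** The two test statistics are treated as bivariate normal with correlation 1/√VIF. The last column is the chance that at least one rejects when there is no effect.

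| D (days) | s (days) | VIF | Power, t-test basis | Power, baseline-adjusted | Error if either model may be reported |
|---|---|---|---|---|---|
| 0 | any | 1.000 | 0.827 | 0.901 | 0.100 |
| 4 | 28 | 1.005 | 0.826 | 0.900 | 0.105 |
| 4 | 14 | 1.020 | 0.821 | 0.896 | 0.110 |
| 6 | 14 | 1.046 | 0.814 | 0.891 | 0.115 |
| 11 | 14 | 1.154 | 0.785 | 0.866 | 0.126 |
| 14 | 14 | 1.250 | 0.760 | 0.845 | 0.132 |
| 21 | 7 | 3.250 | 0.481 | 0.557 | 0.164 |

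The last row is an extreme corner. It needs nearly every HIGRT patient on a full 3-week course, with equal waits in the two arms.

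**3. Target of the coefficient, b ≠ 0.** The section 4 arm coefficient equals the total effect minus b × D/7. The shift is 0.25 × 4/7 = 0.14 or 0.25 × 14/7 = 0.5 points at 0.25 point per week, and 1 × 4/7 = 0.57 or 1 × 14/7 = 2.0 points at 1 point per week.

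Rejection by the section 4 model at 1-sided 0.10 when the total effect is zero (simulation, 12,000 runs, baseline-adjusted with residual SD 8.66, s = 14):

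| D (days) | b = +0.25 | b = −0.25 | b = +1 | b = −1 |
|---|---|---|---|---|
| 4 | 0.091 | 0.112 | 0.058 | 0.162 |
| 14 | 0.065 | 0.142 | 0.015 | 0.365 |

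Without the term the rate is about 0.10 throughout. These departures come from a different estimand, not from ordinary type I error. On the unadjusted SD of 10, 0.162 becomes about 0.15 and 0.365 becomes about 0.31 to 0.32.

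**4. Definition of the covariate.** Section 10.3 bounds the treatment period by the finish of HIGRT or the date of ablation, and that reading is used here. Section 10.4, headed End of Treatment, puts the end of active study treatment 180 days after therapy, which is later than the month-1 outcome.

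**The case against.** Section 2.2.3 belongs to the synopsis, and section 4 is the endpoint section. A shortened synopsis with the fuller section governing is a plausible reading. The onward reference in section 2.2.3 names section 5, which is the study schema, so it is weak evidence of drafting intent. This has some force, but no text states precedence, and section 2.2.3 is a full specification and the place that names the primary analysis as intent-to-treat.

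The term may have a purpose. Section 11.2 times the month-1 survey from completion of treatment, so the baseline-to-survey interval varies between patients. That may be the motive, but the documents do not say so. Because the interval is partly a consequence of assignment, adjusting for it still changes what is estimated. A sensitivity analysis can serve that purpose.

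Deleting the term does not by itself deliver the full effect of assignment. Section 7.4 analyses only patients who received ablation or HIGRT and completed the baseline and month-1 surveys, and section 4 withdraws those who received neither treatment. This stands. The deletion removes one departure from intent-to-treat, not all of them.

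The larger figures rest on assumptions. Gaps of 14 and 21 days exceed the consecutive-weekday counts, and the 0.365 rejection rate needs a 14-day gap and a 1-point-per-week slope of one particular sign. At 4 to 6 days and SD 14 the effect on power and error is small. This also stands and limits the claim about size.

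Finally, only one reading of end of treatment is workable for a month-1 outcome. That is fair, but the covariate still needs a stated definition if it is used anywhere.

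**Conclusion.** The concern holds. The conflict between sections 2.2.3 and 4 is on the page and needs no assumption. It also follows from the plan alone that the added covariate is fixed after randomisation and that its delivery component differs by arm.

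Whether the section 4 coefficient actually departs from the intent-to-treat effect depends on two conditions: a net arm gap in the interval, and a within-arm association between the interval and QOL change. If either is absent, the target is unchanged. If only the association is absent, the cost is precision. The documents do not establish the size or direction of any shift, or that it is severe.

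No stated number is wrong. This should be fixed because it concerns the single primary test, and the correction costs almost nothing.

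**What to change.** In the section 4 primary model, delete the term for time between baseline and end of treatment. Sections 2.2.3 and 4 then both specify arm, baseline global QOL and Child Pugh score, matching the secondary QOL models.

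Report the interval by arm descriptively. If a time-adjusted model is wanted, label it a sensitivity analysis and define end of treatment for it.

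The cost is one sentence of protocol wording, changed before data are analysed by arm. No new data, patients or procedures are needed. Power on the plan's inputs stays at 0.827 before any gain from baseline adjustment, so the accrual target of 90 need not change.
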